****Definition of transfusion dependence and independence for red blood cells (RBC) and/or platelets are described below.**

****maximum remission/response levels correspond to the best values reported in post baseline.*

Transfusions Status Definitions for RBC/platelets

Transfusions for intercurrent diseases not due to MDS (e.g. bleeding, surgical procedure, hemolysis, infections) should not be taken into account for the following:

Transfusion dependence:

1. At baseline: subjects having received ≥ 3 units of transfusion within the 8 consecutive weeks prior to baseline.
2. Post-baseline: subjects having received ≥ 3 units of transfusion within any 8 consecutive weeks during the course of the study.

Transfusion independence:

1. At baseline: subjects having received 0 units of transfusion within any 8 consecutive weeks prior to baseline.
2. Post-baseline: subjects having received 0 units of transfusion within any 8 consecutive weeks during the course of the study.

2.7.1.2 Progression Free Survival

Progression Free Survival (PFS) is defined as time from the date of enrollment (cycle 1 day 1) to disease progression (including transformation to leukemia per WHO 2016 classification), relapse from CR according to modified IWG-MDS or death due to any cause, whichever occurs first, as per investigator assessment.

For subjects without progression, the subject time is censored at the latest date where the subject was known to be alive, without progression and without relapse from CR (on or before the cut-off date).

PFS will be analyzed using the Kaplan-Meier Product-Limit method. Estimates of the 25th, median and 75th percentile of the PFS and their 95% confidence intervals will be provided, Kaplan-Meier curves will be produced, if applicable.

For subjects without PFS event, PFS is censored at last adequate assessment. This is the last response assessment conducted that is not considered as unknown.

The following events could occur after enrollment and may affect the interpretation of the results:

- **Start of further anti-neoplastic therapy:** For a subject without an event before the time he/she receives any further anti-cancer therapy, PFS would be censored at the date of the last adequate assessment prior to start of further anti-neoplastic therapy.

- **Hematopoietic Stem cell transplantation (HSCT):** A subject with an event, regardless of whether it occurred before or after the time he/she receives a HSCT, would be considered as having an event at the date when the event is observed.
- **Stopping study treatment (including due to toxicities):** All events will be taken into account when they occur, regardless of any study treatment interruption or permanent discontinuation.
- **Discontinuation from study due to lost to follow-up or withdrawal of consent:** For subject without an event prior to discontinuation due to lost to follow-up or withdrawal of consent, PFS will be censored at the last adequate assessment date.

For PFS, an event occurring after two or more consecutive missing response assessments (not done or unknown) is censored in the analysis of PFS at the last adequate response assessment before the event date and reason for censoring then summarized as 'Event documented after two or more missing response assessments.'

An exact rule to determine whether there are two missing assessments is therefore needed. This rule will be based on the distance between the last adequate response assessment date and the event date. If the distance is larger than threshold D2 then the analysis will assume that there are two missing assessments. This threshold D2 is defined as two times the protocol specified interval between the response assessments plus the allowed window around the assessments. The protocol defines that response assessment has to be done at least at the time of bone marrow assessments that are to be done every 3 cycles (12 weeks +/- 2 weeks) during the first 12 cycles and every 6 months (+/- 1 month) thereafter. Therefore, for the first 12 cycles, any distance larger than $D2 = 2*14\text{ weeks} = 28\text{ weeks}$ between last adequate assessment and the event means that there are two missing assessments. For the period beyond 12 cycles, any distance larger than $D2 = 2*7\text{ months} = 14\text{ months}$ (56 weeks) means that there are two missing assessments.

The PFS censoring reason will be summarized as:

1. Ongoing without event
2. New anti-neoplastic therapy
3. Withdraw consent
4. Lost to follow-up
5. Event documented after two or more missing response assessments.
6. Discontinuation due to subject/physician/guardian's decision

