## 8 Visit schedule and assessments

Assessment schedules ([Table 8-1](#)) lists all of the assessments and indicates with an “X”, the visits when they are performed. All data obtained from these assessments must be supported in the participant’s source documentation.

No eCRF will be used as a source document.

Each treatment cycle is 28 days. Screening evaluations should be performed within  $\leq$  28 days of Cycle 1 Day 1 (except for the pregnancy test which has to be performed within 72 hours before the first dose). Bone marrow aspirate (BMA) or biopsy performed prior to signing informed consent but within 28 days from the informed consent, may be used. [REDACTED]

[REDACTED] Instead, a viable cryopreserved BMA sample collected prior to informed consent signature (but within 28 days from the informed consent) should be provided, if available.

If the hematology and chemistry laboratory tests are performed within 7 days before enrollment, it is not required to perform them again on C1D1.

During the course of the study visits, test and/or procedures should occur on schedule whenever possible. During the core phase and extension phase, a visit window of  $+\text{-} 7$  days is allowed. During the post-treatment follow up phase a visit window of  $+\text{-}14$  days is allowed.

In case the infusion of MBG453 (sabatolimab), azacitidine or decitabine cannot be administered at the scheduled visit, it has to be administered as soon as possible. Every effort should be made on C1D1 for the drug to be administered on the same day as enrollment. A visit window of  $+7$  days is allowed for treatment administration for reason other than toxicities. [REDACTED]

Participants who discontinue the study treatment for any reason should be scheduled for an end of treatment (EOT) visit within 7 days from the date that the participant discontinued from treatment, at which time all of the assessments listed for the EOT visit will be performed (if bone marrow aspirate or biopsy was performed within 14 days from the EOT visit, the assessment does not have to be repeated).

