## **Extension phase**

Patients completing core phase of 12 months and requiring continuation of study treatment (by investigator decision) beyond 12 months will enter the extension phase. For patients that will receive treatment in the extension phase, they are allowed to continue treatment with MBG453 and azacitidine/decitibine/INQOVI (oral decitibine), azacitidine/decitibine/INQOVI (oral decitibine) alone, or MBG453 alone.

Additionally, for participants who discontinue any study treatment for reasons other than documented disease progression, death, lost to follow-up, or withdrawal of consent, will enter extension phase.

Efficacy assessments (hematology and bone marrow aspirate/biopsy) should follow [Table 8-1](#). Response assessments must continue to be performed every 3 cycles as per hematology assessment and at least every 6 cycles as per bone marrow assessment or as clinically indicated until documented disease progression/relapse (per IWG criteria [Table 8-2](#)), death, lost to follow-up, or withdrawal of consent.

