If the participant cannot or is unwilling to attend any visit(s), the site staff should maintain regular telephone contact with the participant, or with a person pre-designated by the participant. This telephone contact should preferably be done according to the study visit schedule.

For participants who discontinue treatment for reasons other than pregnancy, death, lost to follow-up, or withdrawal of consent, efficacy assessments must continue to be performed every 2 months as per hematology assessment and at least every 6 months as per bone marrow assessment or as clinically indicated until the end of the study, death, lost to follow-up, or withdrawal of consent.

In some circumstances participants may be allowed to continue to receive study treatment beyond disease progression as per criteria described at [Section 6.1.4.1](#). These participants will continue assessments as outlined in the assessments section ([Section 8](#)), and will complete the EOT visit only after permanent discontinuation of study treatment.

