### **9.1.5 Extension phase**

Patients completing core phase of 12 months and requiring continuation of study treatment (by investigator decision) beyond 1 year will enter the extension phase. For patients that will receive treatment in the extension phase, they are allowed to continue treatment with MBG453 and

azacitidine/decitibine/INQOVI (oral decitibine), azacitidine/decitibine/INQOVI (oral decitibine) alone, or MBG453 alone.

Additionally, for participants who discontinue any study treatment for reasons other than documented disease progression, death, lost to follow-up, or withdrawal of consent, will enter the extension phase.

Efficacy assessments (hematology and bone marrow aspirate/biopsy) should follow [Table 8-1](#). Response assessments must continue to be performed every 3 cycles as per hematology assessment and at least every 6 cycles as per bone marrow assessment or as clinically indicated until documented disease progression/relapse (per IWG criteria [Table 8-2](#)), death, lost to follow-up, or withdrawal of consent.

Drug will be supplied as per [section 6.1.4](#) Also patients who will receive HSCT will be included in the extension phase. Patients will be followed up for efficacy and safety as per [Table 8-1](#) up to 24 months post last patient first treatment. Once they complete the extension phase or end treatment due to progression or any reason excluding HSCT, death, lost to follow up, or withdrawal of consent, patients will enter the post-treatment safety follow up. Participants on the extension period can be contacted by telephone every 6 cycles (24 weeks) to follow-up on their survival status.

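### The PFS rule for two missed assessments (threshold D2) has two late values, uses windows the protocol does not give, and names no date to select D2 when a gap crosses cycle 12

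*SAP*

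**What the plan says.** SAP 2.7.1.2 censors an event at the last adequate assessment if it comes after two or more successive assessments were missed. SAP 2.7.3 repeats this for progression, relapse and death. The SAP says this needs a precise rule and measures the gap from last adequate assessment to event against D2, described as twice the protocol's interval plus its window.

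It credits the protocol with response assessments "every 3 cycles (12 weeks +/- 2 weeks) during the first 12 cycles and every 6 months (+/- 1 month) thereafter". From this it takes D2 as 28 weeks for the first 12 cycles. The later value opens "For the period beyond 12 cycles, any distance larger than" and is set at 14 months, glossed as "56 weeks) means that there are two missing assessments".

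Other sections bear on this:

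- **Month length.** SAP 2.1.1.5 fixes a month at 30.4375 days.
- **Windows.** Protocol section 8 gives ±7 days in the sentence starting "During the core phase and extension phase, a visit window of" and ±14 days in the one starting "During the post-treatment follow up phase a visit window of".
- **Late interval.** The Extension phase text in protocol 8.3 asks for response assessment "every 3 cycles as per hematology assessment and at least every 6 cycles as per bone marrow assessment". Protocol 9.1.5 also says "at least every 6 cycles as per bone marrow assessment", and SAP 2.7.1.1 has 6 cycles in extension. Protocol 9.1.1, for participants who stop treatment, says "every 2 months as per hematology assessment and at least every 6 months as per bone marrow assessment".

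**The concern.** D2 decides whether a late-documented progression, relapse or death is an event on its own date or a censored time at an earlier one. Two programmers following the text could assign different statuses to the same patient, for four reasons:

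- The late D2 has two values.
- Its windows are attributed to the protocol but differ from the protocol's.
- Its late interval (months) differs from the extension schedule (cycles).
- Nothing says whether the date of the last adequate assessment or the date of the event selects the early or late D2 when the gap spans the end of cycle 12.

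The last reason matters most, because the choice roughly doubles the threshold and the crossing falls inside the 12-month PFS objective (SAP Table 1-1). SAP 2.7.1 also analyses all available data, so disputed events after 12 months enter the PFS curve.

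**Working it through.** **Inputs.** 28-day cycles (protocol section 3); marrow at C4D1, C7D1, C10D1 and C13D1 (protocol 8.3), nominally days 85, 169, 253 and 337; cycle 12 ends on day 336; 26 cycles end on day 728.

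**The SAP's own figures.**

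- Early D2: 2 × (12 + 2) = 28 weeks = 196 days. This reproduces. Adding the window once, as the wording also allows, would give 2 × 12 + 2 = 26 weeks.
- Late D2: 2 × (6 + 1) = 14 months. 14 × 30.4375 = 426 days = 60.9 weeks. 56 weeks = 392 days. The two differ by 34 days and agree only with 28-day months, 2 × (24 + 4) = 56 weeks, which SAP 2.1.1.5 rules out.

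**Effect of the protocol window.** 2 × (12 + 1) = 26 weeks = 182 days early, not 196. On 6 cycles, 2 × (24 + 1) = 50 weeks = 350 days late, not 392 or 426.

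**Crossing, selected by event date.** The last adequate assessment is C4 (day 85), C7 and C10 are missed, and progression is first seen at the C13 visit. On day 337 the gap is 337 − 85 = 252 days. The late D2 applies, 252 is below 392, and the event is counted although two assessments were missed. Within the C13 visit window (days 330–344), days 330–336 are censored under either selector; days 337–344 split.

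**Crossing, selected by last assessment.** The same patient is censored at day 85, as the two-missed rule intends. But if the last adequate assessment is C10 (day 253), the 28-week value censors every event from day 253 + 197 = 450. With extension marrows 6 cycles after C13 (an assumption), the next after C13 is C19D1, day 505. An event on day 480 is then censored when only C13 was missed. Event-date selection would count it, but would also count events up to day 253 + 392 = 645, or 679 on the 14-month value, well after C19 was missed (day 512 with its window).

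So each selector breaks the two-missed rule somewhere.

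**Size, one patient.** This is a Kaplan–Meier illustration with 39 patients, no other censoring, 12 to 24 events by day 365 at exponential quantiles, and one disputed event on day 340.

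| Events by day 365 | Counted (%) | Censored at day 85 (%) | Difference (points) |
|---|---|---|---|
| 12 | 69.23 | 71.21 | 2.0 |
| 16 | 58.97 | 60.76 | 1.8 |
| 20 | 48.72 | 50.24 | 1.5 |
| 24 | 38.46 | 39.74 | 1.3 |

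A disputed event after day 365, censored instead at C7 or C10, lowers the 12-month rate by 0.3 to 1.1 points through the risk set.

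**The case against.** The strongest reply is that this hardly matters. PFS is secondary and untested. The C4 example needs two successive missed assessments with nothing in between, yet protocol 8.3 requires prompt evaluation of suspected progression, protocol section 8 requires an end-of-treatment visit within 7 days, and SAP 2.7.3 accepts any assessment with a known response status. A 2-point shift is small against a binomial 95% half-width of 1.96 × √(0.25/39), about 16 points at 50% PFS. This stands as to size. It does not make the rule reproducible, and deaths can be learned by survival call without a response assessment. For example, with an end-of-treatment marrow on day 140 and a death on day 400, no new therapy and nothing adequate between, the gap is 260 days: censored under 28 weeks, counted under 56.

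A second reply is that wider windows sensibly allow for shifted cycles: protocol 6.5 lets doses slip by 14 days and cycle starts by up to 56 days. That is a fair reason for ±2 weeks, but the SAP presents it as the protocol's window, not as its own allowance.

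Third, which visits are scheduled response assessments is unclear. SAP 2.7.1.2, protocol 8.3 and Table 8-1 footnote 5 point to C4, C7, C10 and C13. The response row of Table 8-1, as extracted, marks C7, C13 and end of treatment. SAP 2.7.1.1 limits the 3-cycle schedule to the first 7 cycles. This stands, and any replacement D2 depends on settling it.

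**Conclusion.** The rule needs correcting; severity is minor. It is wrong as written, not merely short of detail: the 14-month and 56-week values conflict, the windows are misattributed, and either selector can contradict the two-missed rule. The effect is at most about 2 points on 12-month PFS per disputed patient, under the assumptions shown. How many patients are affected cannot be known from the documents.

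Some stronger readings are tempting but not supported:

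- **The protocol contradicts itself on marrow timing.** Sections 8.3 and 9.1.5 (6 cycles) and 9.1.1 (6 months) all set minimum frequencies, and a 24-week schedule meets both. The mismatch is that the SAP uses 6 months where the extension schedule says 6 cycles.
- **No ±1-month window exists anywhere.** None appears in the available text, but the extension part of Table 8-1 is incomplete as extracted.
- **The 34-day discrepancy matters for everyone.** For a patient last assessed at C13, the gap at the end of extension is 728 − 337 = 391 days, inside both values.
- **Patients with no post-baseline assessment are also misclassified.** The SAP does not say whether baseline counts as adequate, so that cannot be worked out.

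**What to change.** First settle three matters in the text: which visits are scheduled response assessments; whether the late interval is 6 cycles or 6 months; and whether enrollment is the reference date when there is no adequate post-baseline assessment.

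Then delete the 14-month/56-week pair. State D2 in days, select it by the date of the last adequate assessment, and derive it from the next two scheduled response assessments. Use the protocol's ±7 days, or keep ±2 weeks but call it the SAP's own allowance for shifted cycles. If the 3-cycle core and 6-cycle extension marrow schedule is confirmed, with extension marrows counted from C13D1:

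| Last adequate assessment | ±7 days | ±2 weeks |
|---|---|---|
| C4 or C7 | 13 + 13 = 26 weeks, 182 days | 14 + 14 = 28 weeks, 196 days |
| C10 | 13 + 25 = 38 weeks, 266 days | 14 + 26 = 40 weeks, 280 days |
| C13 or later | 25 + 25 = 50 weeks, 350 days | 26 + 26 = 52 weeks, 364 days |

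The SAP's document history dates the current addendum after database lock. Label the change post-lock, show the result under the existing text alongside (saying which reading of it was programmed), and footnote how many PFS statuses differ. If none do, the footnote closes the matter.

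The cost is SAP wording, one derivation and one footnote; no new visits or data. The downside is that a few statuses may change after lock, and the narrower window would move some counted events to censored.

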2.7.1.3 Overall Survival

Overall Survival (OS) rate is defined as the proportion of subjects alive time from the date of enrollment (cycle 1 day 1) to date of death due to any cause.

If a subject is not known to have died, then OS will be censored at the latest date the subject was known to be alive (on or before the cut-off date). All deaths will be taken into account whenever the death occurred, i.e. even after new anti-neoplastic therapy, HSCT, interruptions, or discontinuation of study treatment due to any reason.

The OS censoring reason will be summarized as 'Alive' or 'Lost to follow-up'. Subjects not known to have died will have the censoring reason 'Lost to follow-up' if the reason for discontinuation from study is 'Lost to follow-up' or 'Withdrawal of consent'.

Otherwise, subjects will have the censoring reason 'Alive'.

OS will be analyzed using the Kaplan-Meier Product-Limit method. Estimates of the 25th, median and 75th percentile of the OS and their 95% confidence intervals will be provided, Kaplan-Meier curves will be produced, if applicable.

2.7.1.4 Leukemia-free survival

Leukemia-free survival (LFS) is the time from the date of enrollment (cycle 1 day 1) to $\geq 20\%$ blasts in bone marrow/peripheral blood (per WHO 2016 classification) or death due to any cause.

For a subject without event, the subject is censored at the latest date the subject was known to be alive and without leukemia (last adequate assessment, bone marrow and/or hematology assessment on or before the cut-off date).

LFS will be analyzed using the Kaplan-Meier Product-Limit method. Estimates of the 25th, median and 75th percentile of the PFS and their 95% confidence intervals will be provided, Kaplan-Meier curves will be produced, if applicable.

2.7.1.5 Response Rates

Response rate is defined as the proportion of subjects with best overall response of either complete remission (CR)/marrow remission (mCR)/partial remission as per investigator assessment according IWG- MDS at any time during the study (on or before cut-off date) ([Table 2-6](#)). The number and percentage of subjects with all other responses rates will be summarized.

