#### **6.1.4.1 Treatment beyond disease progression**

Participants with immunotherapy may get clinical benefit despite initial evidence of disease progression. Participants will be allowed to continue the study treatment, (HMA and/or MBG453 (sabatolimab)) beyond disease progression through the extension phase if all four of the following criteria are met:

1. Absence of acute leukemia per WHO 2016 classification (as defined as  $\geq 20\%$  of blasts in bone marrow and/or peripheral blood) ([Arber et al 2016](#))
2. There is a clinical benefit observed per investigator assessment. The clinical benefit at the time of disease progression should consist of :
  - Improved or stable ECOG performance status and no cell lineage (neutrophils count, platelets count, hemoglobin) have worsened by  $>25\%$  as compared to baseline status
  - And, at least one of the two following criteria:
    - Improvement or stabilization of cytopenia in at least one cell lineage (neutrophils count, platelets count, hemoglobin) as compared to baseline values, or
    - Reduction of RBC/platelet transfusion needs within the 8 weeks prior to evidence of disease progression as compared to transfusion needs reported prior to enrollment
3. No unacceptable toxicity is reported
4. The participant continues to follow all protocol requirements

In addition, treatment beyond disease progression should not jeopardize critical interventions to treat/prevent severe complications or prevent participants from receiving adequate care.

If the study treatment continues, the participants should continue to perform all assessments for extension phase as per [Table 8-1](#).

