2.7.1 Secondary endpoints

Following are the secondary endpoints to be considered for analysis by 12 months post LPFT and for complete available data for the study. Additionally for OS analysis by 24 months post LPFT will also be analyzed.

A listing of all responses assessments by subject will be provided including BOR, PFS time, PFS event (yes/no), OS time, death date and duration of CR. Bone marrow blasts percentage will also be listed. In addition, for some selected laboratory parameters and for bone marrow blasts percentage, trends over time will be displayed via boxplots and corresponding tables displaying the summary statistics for these selected timepoints to be produced.

2.7.1.1 Complete remission rate:

Complete remission rate will be assessed according to International Working Group (IWG) for MDS (2006) with MBG453 (sabatolimab) in combination with HMAs (IV/SC/Oral) in subject with intermediate, high, or very high risk MDS.

Proportion of subjects achieving CR will be presented together with an exact 95% confidence interval.

A sensitivity analysis may be performed for CR by considering IWG-MDS & modified IWG-MDS of Peripheral blood.

If any subject who achieved CR and discontinued/lost to follow-up within 12 months will be considered as Responder.

If any subject who achieved CR and undergone to Bone Marrow Transplantation (BMT) within 12 months will be considered as Responder.

Subjects who discontinue early before achieving response will be considered as non-responders. Similarly subjects with transplant or subjects with progression before achieving response will be considered as non-responders. As appropriate, additional sensitivity analyses will be performed excluding discontinued subjects, transplant subjects and subjects with progression before documentation of CR.

Response assessment rules

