Response assessment will be performed by the investigator according to the assessment schedule depicted in protocol Table 8-1 based on available bone marrow assessment and peripheral blood every 3 cycles for core phase during the first 07 cycles and every 6 cycles for extension phase and all transfusions records as detailed in [Table 2-6](#) using the modified version of the published response criteria IWG for MDS. Moreover, response assessments can be performed at any time if clinically indicated, e.g. for confirmation of response but also for any suspicion of progression/relapse. These assessments are recorded as an unscheduled visit in the eCRFs and will be considered for the overall determination of response and progression/relapse with the respective assessment date.

The investigator does not determine best overall response, he/she is assessing only the response based on the given bone marrow and peripheral blood data, the history of transfusions and myeloid growth factor received within the last 2 weeks.

The best overall response (BOR) will be derived based on the CR secondary endpoint rules by Novartis as below:

- CR = at least one determination of CR without progression or relapse from CR within the four after CR.
- mCR = at least one determination of mCR (and not qualifying for a CR).
- PR = at least one determination of PR (and not qualifying for a CR/mCR).
- SD = at least one SD assessment and not qualifying for CR, mCR or PR.
- PD = progression after enrollment and not qualifying for CR, mCR, PR or SD.
- UNK = all other cases (i.e., not qualifying for confirmed CR or mCR or PR and without SD or progression).

Details on the definition of response categories which are to be captured in the eCRF by the investigator were defined in Table 8-2 of the protocol that was copied into Table 2-6 below.

Table 2-6 Modified response classification per IWG criteria in MDS

| Response category | Definition [#] |
|-------------------|-------------------------|
|-------------------|-------------------------|

| | |
|--|--|

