2.7.1.7 Time to Complete Remission

Time to Complete Remission is defined as the time from the date of enrollment (cycle 1 day 1) to the first documented CR.

Time to complete remission will be analyzed using the Kaplan-Meier Product-Limit method. Subjects who are known to be without CR will be censored at study-maximum follow-up time (i.e. Last Subject Last Visit (LPLV) for final analysis, for analysis of cut-off date min (LPLV, Cut-off date)) for subjects with a PFS event (i.e. disease progression or death due to any cause), or at the date of the last adequate assessment for subjects without a PFS event. Estimates of the 25th, median and 75th percentile of the time to CR and their 95% confidence intervals Kaplan-Meier plots will be provided, if applicable. Improvement in RBC/platelets transfusion independence

The number and percent of subjects who are RBC/platelets transfusion independent after the date of enrollment as per IWG-MDS will be provided.

RBC/Platelets transfusion independence rate is defined as the proportion of subjects having received <0 units (no RBC/Platelets transfusions) during at least 8 consecutive weeks after enrollment ([Table 2-6](#)). The number and percentage of subjects will be shown for the overall FAS and then also in only those with transfusion dependence at baseline. Percentages will be provided with exact 95% Clopper-Pearson confidence intervals. Bar graphs will be provided.

For subjects with at least one period of transfusion independence post-baseline, the total duration of all transfusion independence periods (which all individually must be at least 8 weeks) will be also summarized.

The duration of each period of transfusion independence is defined from the end date of the last transfusion received until the date transfusions are given again or last date of treatment administration in case transfusions had not (re-)started during treatment. The total duration of all transfusion independence periods is the sum of each period of the transfusion independence.

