2.7.3 Handling of missing values/censoring/discontinuations

Missing data for safety and efficacy endpoints will not be imputed.

For the determination of CR, only assessments post enrollment and prior start of any other anti-neoplastic therapy or HSCT are considered.

For the determination of PFS events, only assessments post enrollment and prior start of any other anti-neoplastic therapy are considered. If disease progression/relapse from CR or death is documented after two or more missing response assessments, PFS will be censored at the last adequate response assessment prior to the event.

For PFS and duration of CR, an adequate response assessment is considered any disease assessment indicating response status apart from “unknown” or “not done”.

A subject whose disease has not progressed or died by the date of the analysis cut-off will have their PFS censored at the time of the last adequate tumor evaluation performed on or before the cut-off date. Clinical deterioration will not be considered as documented disease progression.

Further details were already described in [Section 2.7.1](#).

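### The SAP cuts CR at new anti-neoplastic therapy or HSCT but writes no cut for mCR, PR, SD or the transfusion-independence rate, so later outcomes could be counted for the combination

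*SAP*

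**What the plan says.** **CR.** SAP 2.7.3 states: "For the determination of CR, only assessments post enrollment and prior start of any other anti-neoplastic therapy or HSCT are considered". SAP 2.7.1.1 adds two rules for the CR rate: "Subjects who discontinue early before achieving response will be considered as non-responders" and "Similarly subjects with transplant or subjects with progression before achieving response will be considered as non-responders".

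**BOR.** Also in 2.7.1.1: "The best overall response (BOR) will be derived based on the CR secondary endpoint rules by Novartis as below". The rules that follow are bullets. The second reads "mCR = at least one determination of mCR (and not qualifying for a CR", and those for PR and SD have the same form. The CR bullet excludes progression or relapse that follows the CR.

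**Response rate.** SAP 2.7.1.5 takes subjects whose BOR is CR, mCR or PR, "according IWG- MDS at any time during the study (on or before cut-off date".

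**Transfusion independence.** The text that runs on from SAP 2.7.1.7 counts subjects without transfusion "during at least 8 consecutive weeks after enrollment". The duration of a period in which transfusions did not restart on treatment ends at the last treatment administration.

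**Follow-up.** Protocol section 3 continues response assessments in participants who stopped treatment for transplantation, and 9.1.5 places HSCT patients in the extension phase with efficacy follow-up. Protocol 6.2.1 and the post-treatment rows of Table 8-1 collect transfusions after treatment. Protocol 6.1.4.1 lets selected participants continue study drug "beyond disease progression through the extension phase if all four of the following criteria are met".

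**The concern.** In a single-arm trial, the response and transfusion-independence rates are read as activity of sabatolimab plus HMA, with no comparator to offset a bias. The window for a response therefore has to be explicit. Here it is explicit for CR and PFS only. Followed literally, the text lets a remission or transfusion-free spell that first appears after a transplant or a new drug enter the combination's rate. It also lets one participant be a non-responder in the CR rate and a CR in the BOR table of the same report.

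**Working it through.** The plan gives no figure for these endpoints that could be reproduced, and no test is planned (SAP 2.7.2). The check sets the written windows side by side.

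| Outcome | Stop at new therapy | Stop at HSCT | Progression before response |
|---|---|---|---|
| CR rate (2.7.1.1, 2.7.3) | yes | yes | non-responder |
| BOR = CR (2.7.1.1, 2.7.3) | yes | yes | not repeated |
| BOR = mCR, PR, SD (2.7.1.1) | not written | not written | not written |
| Response rate (2.7.1.5) | not written | not written | not written |
| PFS events (2.7.1.2, 2.7.3) | yes | no | is itself the event |
| Transfusion-independence rate | not written | not written | not written |

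The PFS row shows that the SAP sets windows endpoint by endpoint: PFS is not cut at HSCT, and CR is. A programmer therefore cannot assume one common window.

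**Path 1: mCR after transplant.** A participant without CR goes to HSCT. A later marrow shows at most 5% blasts and a fall of at least 50% from baseline. SAP 2.7.3 bars this as a CR. It meets the marrow definition of mCR in Table 2-6, which needs no blood-count recovery. The mCR bullet asks for one determination and no CR, so the participant can enter the 2.7.1.5 rate.

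**Path 2: CR after progression.** A participant progresses, continues study drug under Protocol 6.1.4.1, then reaches CR. The CR rate makes this a non-response. The BOR = CR bullet looks only at progression or relapse after the CR, so it can return CR.

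**Path 3: transfusion-free spell after treatment.** A spell that begins after the last dose and lasts 8 weeks counts in the rate. Its duration runs from the last transfusion to the last treatment date, which is earlier, so it is negative. A spell that begins less than 8 weeks before the last dose can also count in the rate, yet have a duration below the 8 weeks that the SAP requires of each period.

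**Weight of mCR.** In the earlier HR-MDS data in Protocol Table 1-4, mCR made up 4 + 1 + 3 = 8 of 6 + 4 + 6 = 16 remissions. Protocol 4.3.2 gives 3 mCR to 6 CR with decitabine and 7 mCR to 2 CR with azacitidine. The category without a written cut is not a marginal one.

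**Size.** With 39 enrolled (SAP 1.1), and all 39 assumed to be in the FAS, one participant moves a rate by 1/39 = 0.0256, or 2.6 percentage points. In the subset that is transfusion dependent at baseline the step is larger, because the denominator is smaller; the documents do not give it. For scale, from an assumed 16/39 = 41.0% (exact 95% CI 25.6 to 57.9), one extra responder gives 17/39 = 43.6% (27.8 to 60.4).

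**The case against.** The best defence is the BOR lead-in, which ties BOR to the CR endpoint rules. The bullets sit in the same section as the non-responder rules, and those speak of response rather than CR. Read together, a participant who first reaches mCR after HSCT is a non-responder, and the disagreement between CR rate and BOR disappears. This reading is reasonable, so inheritance by mCR and PR is unclear rather than absent. It does not settle the matter: the lead-in points to the rules listed below it, those rules contain no cut, and 2.7.1.5 then uses an open window.

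For transfusion independence, ending an open period at last treatment suggests an on-treatment concept. The rate sentence does not say so.

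Three stronger readings are tempting and should be resisted.

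- A reader might infer that BOR and the response rate have no stop at all. For CR that is wrong: 2.7.1.1 and 2.7.3 exclude a CR reached only after HSCT or new therapy.
- A reader might treat a response after progression as rescue. Under Protocol 6.1.4.1 the participant is still on study drug, so whether it counts is a choice of estimand. Only the inconsistency between the CR rate and BOR is a defect.
- A reader might assume 2 to 4 affected participants, or 5.1 to 10.3 points. No HSCT or post-therapy response count is given, and Protocol 5.1 enrolls patients unsuitable for immediate HSCT at screening.

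Assessment after progression is also not settled. Protocol section 3, 8.3 and 9.1.5 stop response assessment at progression; 9.1.1 runs efficacy assessment to the end of the study. Systematic marrow data after second-line therapy for progression cannot be presumed.

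Finally, the endpoints are descriptive. SAP 2.7.1 lists all response assessments by subject with BOR, and 2.4.2 summarizes later anti-neoplastic therapy and HSCT. Affected cases can therefore be traced.

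**Conclusion.** The point holds as a gap in definition that can raise two reported rates. As written, mCR or PR first seen after HSCT or new therapy could count in the response rate, and a transfusion-free spell after either could count in the transfusion-independence rate. The CR rate is protected, though BOR = CR could disagree with it after progression. The size is 2.6 points per affected participant, assuming an FAS of 39. The number affected cannot be derived from the documents and may be zero. Sample size, alpha and power are untouched. The conclusion rests on post-transplant response assessments and post-treatment transfusion records being collected, as the protocol plans.

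**What to change.** - **SAP 2.7.3:** widen the CR sentence to *BOR and every response category (CR, mCR, PR, SD)*, with the same stop at other anti-neoplastic therapy or HSCT.
- **SAP 2.7.1.5:** replace the open window with that one.
- **SAP 2.7.1.1:** state that the BOR rules apply the same progression-before-response rule as the CR rate.
- **Transfusion independence:** end the window for the rate at the earlier of other anti-neoplastic therapy or HSCT.
- **Reporting:** list later responses and transfusion-free periods separately, labelled as occurring after HSCT or new therapy.
- **Protocol:** reconcile 8.3 and 9.1.5 with 9.1.1 on efficacy assessment after progression.

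The SAP document history dates the current addendum after database lock, so the change must be labelled as made after lock. It costs SAP wording and a derivation filter, and needs no new data. The downside is that the reported rates may be slightly lower.
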